SARS-CoV-2 Severe acute respiratory syndrome – coronavirus 2

SES Socioeconomic status VE Vaccine effectiveness

Executive summary

The end of 2019 saw the emergence of a novel severe acute respiratory syndrome coronavirus 2 (SARS-CoV-2) causing coronavirus disease 2019 (COVID-19). As of October 2023, almost 276 million cases and more than 2.2 million deaths had been reported in the WHO European Region [1]. As of October 2023, eight vaccines (Comirnaty, COVID-19 Vaccine Valneva, Nuvaxovid [previously Novavax], Spikevax [previously COVID-19 vaccine Moderna], Vaxzevria [previously AstraZeneca], Jcovden [previously Covid-19 Vaccine Janssen], VidPrevtyn Beta [from Sanofi] and Bimervax [previously COVID-19 Vaccine HIPRA]), Nuvaxovid (NVX-CoV2373) and six adapted vaccines (Comirnaty Original/Omicron BA.1, Spikevax bivalent Original/Omicron BA.1, Comirnaty Original/Omicron BA.4-5, Spikevax bivalent Original/Omicron BA.4-5, Comirnaty Omicron XBB.1.5 and Spikevax XBB.1.5 have been authorised by the European Commission based on the scientific opinion of the European Medicines Agency (EMA) for use in the European Union, and many others are under rolling review [2].

Influenza viruses undergo frequent genetic and antigenic changes. The influenza vaccine is reformulated each year and annual re-vaccination is recommended. Observed influenza vaccine effectiveness (IVE) varies from year to year between population sub-groups (age groups, risk groups) and differs for the various influenza types, subtypes and genetic clades, and outcomes measured. Immunological correlates of protection are not well defined. In 2017, the EMA formally adopted new guidelines on influenza vaccines covering, inter alia, post-authorisation studies of vaccine effectiveness, including brand-specific IVE data [3].

The available vaccine products currently in use for EU/EEA immunisation programmes, the target groups for vaccination and the vaccination coverage all vary across countries. New vaccines are being developed for which limited or no effectiveness data are yet available in the EU. A comparison by vaccine type (adjuvanted vs non-adjuvanted, live attenuated vs inactivated, egg- vs cell-based, high vs standard dose), group (split virion, subunit, etc.) and product could provide essential information for vaccine recommendations and health economic assessments.

In 2020, the European Commission stressed the importance of continuously monitoring the safety and effectiveness of vaccines in the EU/EEA in the post-authorisation phase, with particular emphasis on COVID-19 vaccines in the context of the ongoing pandemic [4]. The 2018 'Council Recommendation on Strengthened Cooperation against Vaccine-preventable Diseases' already called on the European Centre for Disease Prevention and Control (ECDC) and EMA to cooperate to ensure the continued monitoring of vaccines and vaccination in use in EU/EEA vaccination programmes [5]. This request was subsequently formalised as part of the extended EMA regulatory mandate [6] and ECDC's newly amended mandate [7], requiring the two agencies to develop a structured and independent post-authorisation vaccine monitoring platform, initially prioritising COVID-19 vaccines. ECDC and EMA officially established and launched the platform in May 2022, with the intention of bringing together public health and regulatory experts to discuss the studies needed to generate real-life evidence on the safety and effectiveness of vaccines in use in EU/EEA immunisation programmes.

From 2020, ECDC began building the infrastructure to perform COVID-19 vaccine effectiveness (CVE) studies, using the lessons learned from other vaccine effectiveness studies already conducted. One such study was the ECDC-funded I-MOVE (Influenza – Monitoring Vaccine Effectiveness in Europe) project, under which influenza vaccine effectiveness (IVE) has been measured in Europe using primary care sentinel surveillance systems since the 2007/08 influenza season [3,4]. The infrastructure will be used to build a system that regularly monitors vaccine effectiveness and performs studies, including impact and burden of disease studies, in different settings. Depending on the setting, information will be provided on different outcomes (severe disease, moderate disease, transmission, etc). The overall project is called VEBIS (Vaccine Effectiveness, Burden and Impact Studies) and it includes different networks of study sites/countries/infrastructures, where the multi-country studies are conducted.

This core protocol for ECDC studies of VE against hospitalisation with severe acute respiratory infection (SARI) laboratory-confirmed with SARS-CoV-2 or with influenza, version 3.0, represents an update to the main elements for a multi-country hospital-based study of COVID-19 vaccine effectiveness in patients hospitalised with SARI, initially published as version 1.0 [5], updated to version 2.0 [6]. This version includes updates on methodology for CVE pooled analyses The larger sample size achieved by combining data from multiple sites will provide more statistical power to meet more specific objectives. The protocol can be implemented for COVID-19 and/or influenza.

The proposed method is a case-control study using a test negative design. The study population consists of individuals of all ages, belonging to the target group for COVID-19 or influenza vaccination, hospitalised with SARI symptoms and no contra-indication for being vaccinated with the vaccine of interest. It would be beneficial if countries test for all other respiratory viruses (as appropriate depending on time of year).

This core protocol is primarily intended to guide the implementation of ECDC-funded studies. However, ECDC encourages using this protocol as a basis to conduct vaccine effectiveness studies in countries not currently planning to participate in ECDC-funded studies. The use of consistent protocols will facilitate the comparability of study results across studies, countries and study sites.

1. Background

1.1 COVID-19

The end of 2019 saw the emergence of a novel severe acute respiratory syndrome coronavirus 2 (SARS-CoV-2) causing coronavirus disease 2019 (COVID-19), As of October 2023, almost 276 million cases and more than 2.2 million deaths had been reported in the WHO European Region [1]. As of October 2023, eight vaccines (Comirnaty, COVID-19 Vaccine Valneva, Nuvaxovid [previously Novavax], Spikevax [previously COVID-19 vaccine Moderna], Vaxzevria [previously AstraZeneca], Jcovden [previously Covid-19 Vaccine Janssen], VidPrevtyn Beta [from Sanofi] and Bimervax [previously COVID-19 Vaccine HIPRA]), Nuvaxovid (NVX-CoV2373) and six adapted vaccines (Comirnaty Original/Omicron BA.1 [authorised 1 September 2022], Spikevax bivalent Original/Omicron BA.1 [1 September 2022], Comirnaty Original/Omicron BA.4-5 [12 September 2022], Spikevax bivalent Original/Omicron BA.4-5 [20 October 2022], Comirnaty Omicron XBB.1.5 [31 August 2023] and Spikevax XBB.1.5 [15 September 2023]) have been authorised by the European Commission based on the scientific opinion of the European Medicines Agency (EMA) for use in the European Union, and many others are under rolling review [2]. Comirnaty and Spikevax vaccines of three different valencies have now been approved: a monovalent vaccine based on the original SARS-CoV-2 strain, a bivalent vaccine based on the original strain and the Omicron BA.1 lineage, and a bivalent vaccine based on the original strain and the Omicron BA.4-BA.5 lineages, and an adapted vaccine based on Omicron XBB.1.5. [2]. Some EU/European Economic Area (EEA) countries have also used other vaccines, such as Sputnik V and Sinopharm in Hungary.

By January 2021, all 30 EU/EEA countries had started COVID-19 vaccination campaigns, and different COVID-19 vaccine products have been gradually introduced as they have become available through the EU Vaccines Strategy [8]. In addition to healthcare workers and residents of long-term care facilities, the vaccination strategy in the general population had an age-based staggered approach prioritising older individuals over younger ones. Most of the vaccines used so far, including booster vaccines, have been mRNA vaccines [9].

1.2 Influenza

Despite a recommendation in 2009 by the Council of Ministers that all EU Member States achieve an influenza vaccination coverage of 75% in all risk groups by the winter season 2014–15, a survey by ECDC at the end of 2018 showed that very few had reached this goal in the specific risk groups [10]. Risk groups are defined as children aged 6–59 months, pregnant women, healthcare workers, individuals 60 or 65 years and older, and people with a range of underlying medical conditions [11,12].

Influenza viruses undergo frequent genetic and antigenic changes and vaccine-induced immunity only lasts between 6–12 months (sometimes less). Therefore, the influenza vaccine is evaluated each year and annual revaccination is recommended. Available seasonal influenza vaccines are only moderately effective and influenza vaccine effectiveness (IVE) may vary depending on the vaccine product, the time since last vaccination and previous influenza infection and influenza vaccine history. Observed IVE varies from year to year among population sub-groups (age groups, risk groups) and differs for the various influenza types, subtypes, antigenic groups and outcomes measured.

Conducting annual IVE estimates at the European level right at the beginning of a seasonal influenza epidemic/pandemic may provide critical evidence for public health recommendations. For example, the recommended target groups for the current season's vaccine can be expanded/amended if circulating strains are causing severe illness, but there are good/high early IVE estimates. Alternatively, very low early IVE estimates can prompt recommendations to use other non-pharmaceutical interventions (such as use of face masks or physical distancing), or antivirals as an additional preventative measure. Lacking early season IVE results could also result in a failure to use alternative measures, leading to increased disease burden and increased costs.

Monitoring of the IVE along the course of the epidemic/pandemic allows more precise estimates of the impact of current vaccination strategies on the burden of disease to support vaccination campaigns, and may trigger further investigations on seasonal and pandemic vaccines (improve composition, use of adjuvants, different doses, or the need for booster doses). Additionally, IVE studies can counterbalance the reports of adverse events following immunisation by providing elements for adequate risk benefit and cost-effectiveness analysis.

Early-season IVE by product and influenza type/subtype is also critical for the WHO vaccine composition meeting discussions, in which the vaccine selections for the subsequent season are decided.

Furthermore, new vaccines are being developed for which limited or no effectiveness data are yet available in the EU. In the event of an influenza pandemic, an established EU platform to rapidly measure IVE by vaccine type and product will allow the evaluation of any pandemic vaccine and the adaptation of preventive and control strategies.

Besides measuring IVE by influenza (sub)type early and late in the season and by vaccine type, these IVE studies can be used to help answer further research questions, such as the effect of previous influenza vaccination on current season influenza infection, to what extent IVE may decline within the season, the effect of first influenza infection on subsequent IVE and the measurement of IVE against different influenza clades or genetic variants.

Long-term multi-centre studies may provide adequate sample size and data quality to answer some of these questions.

1.3. Integrated respiratory surveillance

It is recommended that surveillance for respiratory pathogens (including both influenza and SARS-CoV-2) should be integrated across Europe [13,14]. Effective integrated respiratory surveillance systems should provide data sufficient for monitoring the spread and intensity of respiratory viruses to guide control measures and mitigate their impact. These systems will also be important in the event of future pandemics. In this context, well-designed, representative sentinel surveillance systems in primary and secondary care should remain the central surveillance method for acute respiratory infections. Sentinel systems provide robust epidemiological data that are routinely collected using common syndromic case definitions with reliable denominators and integral microbiological testing that can be extended to multiple viruses. This makes them ideal as the basis of integrated impact assessment of influenza, COVID-19, and potentially other respiratory virus infections. Monitoring systems should be sensitive enough to detect virus variants, accurately follow virus-specific disease incidence by age/location/level of severity and to assess vaccine effectiveness.

1.4 ECDC COVID-19 and influenza vaccine effectiveness studies

In 2018, the Council 'Recommendation on Strengthened Cooperation against Vaccine-preventable Diseases' (2018/C 466/01) called on the European Commission to work with the Member States, with the support of EMA and in cooperation with ECDC, to '... continuously monitor the benefits and risks of vaccines and vaccinations at EU level, including through post-marketing authorisation studies'. In 2020, the European Commission stressed the importance of continuously monitoring the safety and effectiveness of vaccines in the EU/EEA in the post-authorisation phase, with particular emphasis on COVID-19 vaccines in the context of the ongoing pandemic [15]. This was subsequently formalised as part of the extended EMA regulatory mandate [16] and ECDC's newly amended mandate [17], requiring the two Agencies to develop a structured and independent post-authorisation vaccine monitoring platform, initially prioritising COVID-19 vaccines. ECDC and EMA officially established and launched a platform in May 2022, with the intention of bringing together public health and regulatory experts to discuss the studies needed to generate real-life evidence on the safety and effectiveness of vaccines in use for EU/EEA immunisation programmes.

ECDC began building infrastructure to perform COVID-19 vaccine effectiveness (CVE) studies in 2020, using the lessons learned from other vaccine effectiveness studies (Table 1). The infrastructure is being used to build a system that regularly monitors CVE and performs studies in different settings. Depending on the setting, information will be provided on different outcomes (severe disease, moderate disease, transmission, etc). At the start of 2022, ECDC expanded this infrastructure to include IVE monitoring. The multi-country approach of effectiveness studies is one of the key features, and other countries are foreseen to be included over time.

Table 1. Type of studies and settings within the VEBIS infrastructure, as of November 2023

Setting	Type of study	Main outcome	References
Hospitals	Test negative design	Severe disease; influenza and COVID-19	[5,6,18–22]
Healthcare workers cohort	Cohort study	Infection, COVID-19	23,24]
Electronic healthcare databases	Cohort study	Hospitalisation, death, COVID-19	[25]
Primary care	Test negative design	Moderate disease (~ARI/ILI), influenza	[26,27]
·		and COVID-19	

One of the first studies implemented, and for which the core ECDC protocol version 1.0 was published in October 2021 [8], was a multi-country study to estimate CVE against severe disease, by assessing it in individuals hospitalised for SARI. The second update is presented in this document as version 3.0.

1.5 Aim of the core protocol

This core protocol for ECDC studies of CVE and IVE against hospitalisation with SARI laboratory-confirmed with SARS-CoV-2, and SARI laboratory-confirmed with influenza, version 3.0, presents the main elements for a multi-centre (multi-country) hospital-based study of CVE/IVE in patients hospitalised with SARI. It outlines the agreed methods for collecting data related to SARS-CoV-2, COVID-19 and influenza virus and disease at country level, and includes a plan for the pooled analysis. The combination of data from multiple sites will facilitate studies with more statistical power in order to meet more specific objectives.

ECDC has worked closely with EU Member States with to implement a system for the regular monitoring of vaccine effectiveness among hospitalised SARI patients, taking advantage of parallel efforts to enhance SARI surveillance in the EU/EEA and countries of the Western Balkan region¹. Hospitals that can apply the core protocol and contribute to EU-level monitoring of CVE and ultimately IVE have been recruited through a process involving ECDC's relevant National Coordinator².

This core protocol is therefore primarily intended to guide the implementation of ECDC-funded studies. However, ECDC encourages using this protocol in countries not currently planning to participate in ECDC-funded studies.as a basis to conduct VE studies , as the use of consistent protocols will facilitate the comparability of study results across studies, countries, and study sites.

This document presents version 3.0 of the core protocol. Version 2.0 has already been implemented at country level. This document will be updated and revised on a regular basis.

This core protocol is complemented by a questionnaire, a list of variables to be collected and their coding, all of which are available upon request at [contact] (the list of variables and coding also appear in Annex 1).

Under each paragraph, arrow marks indicate the points that countries/hospitals/study sites could further expand/detail when creating a country-specific protocol using the core ECDC protocol.

4

¹ Western Balkans, i.e. Albania, Bosnia and Herzegovina, Montenegro, Serbia, North Macedonia, and Kosovo (this designation is without prejudice to positions on status, and is in line with UNSCR 1244/1999 and the ICJ Opinion on the Kosovo declaration of independence).

² https://www.ecdc.europa.eu/sites/portal/files/media/en/aboutus/governance/competent-bodies/Documents/coordinating-competent-bodies-structures-terms-of-reference-and-interactions-w-Annexes.pdf

2. Objectives

2.1 Primary objective

The primary objective of this protocol is for it to be used to measure the direct effect (effectiveness) of overall and product-specific COVID-19 and influenza vaccines against SARI due to laboratory-confirmed SARS-CoV-2 and/or influenza in hospitalised patients, within each European country/site participating in both CVE and IVE and in a pooled, multi-country analysis. This will provide up-to-date information on the ability of COVID-19 and influenza vaccines to prevent severe disease under real conditions of use.

2.2 Secondary objectives

The secondary objectives are among SARI patients requiring hospitalisation:

- to measure overall and product-specific CVE and IVE against SARI due to laboratory-confirmed SARS-CoV-2 or influenza in hospitalised patients by participating study country, risk group (e.g. specific chronic conditions), age group, COVID-19 or influenza vaccination target group, time since vaccination, calendar time and vaccine doses when applicable;
- to measure overall and product-specific CVE and IVE against specific genetic variant(s) of laboratory-confirmed SARS-CoV-2, type, subtype/lineage and specific clades of influenza (where possible), and more severe outcomes (ICU admission, invasive ventilation, in-hospital mortality);
- to identify potential factors that may modify CVE or IVE: prior SARS-CoV-2/influenza infection, chronic conditions, the role of influenza/COVID-19 vaccination, etc.

The aim of these three secondary objectives is to understand the duration of vaccine protection and identify any differences in CVE/IVE among each of these strata, potential target groups for vaccination, and key SARS-CoV-2 or influenza virus phenotypic or genotypic evolutions that could affect vaccine performance.

2.3 Specific objectives for COVID-19 vaccine effectiveness

The estimation of CVE has evolved compared to the VE when COVID-19 vaccination was first introduced. There has been much variation in the scientific literature in the past two to three years in the definitions of vaccination and reference groups used. In this protocol, we focus on an analysis of CVE for a specific seasonal vaccination campaign, similar to IVE. Here we compare the group vaccinated during the seasonal COVID-19 vaccination campaign of interest with a group not vaccinated during the vaccination campaign of interest. This provides information on the performance of the current season's vaccine(s), not taking prior vaccination history into account and providing, for the exposed group, a potentially similar exposure in a context of constantly changing variants. COVID-19 is still a novel virus, and our approach to analyse CVE will evolve over time, with several reference groups currently relevant. We propose other analysis types alongside the main analysis. More details can be found in Sections 3.8 Exposure (vaccination) and 3.13 Analysis.

- Each study site/country to specify primary objectives of their study as measuring CVE only or CVE and IVE.
- Each study site/country to specify the (additional) secondary objectives of their study.

3. Methods

3.1 Study design

The following study design is applied:

At country level: a hospital-based, test-negative, case-control study at each participating hospital.

 At EU/EEA level: a multi-centre hospital-based, test-negative, case-control study, using pooled data from several countries/regions.

In addition to the test-negative controls, some sites/countries may be able to recruit a second additional control group (e.g. non-SARI hospitalised patients matched to cases by date of admission; see Section 3.5.5).

Each study site/country to specify if, in addition to the test-negative controls, other control groups are selected.

3.2 Study population

This study is intended to be conducted primarily in countries with pre-existing SARI surveillance systems, to recruit patients for hospital-based CVE/IVE studies. The study population for the CVE/IVE study will therefore consist of individuals of all ages hospitalised with SARI symptoms in one of the participating hospitals/services, with no contra-indication for COVID-19 vaccination (for CVE studies) or for influenza vaccination (for IVE studies).

- Each study site/country to describe the setting (number of hospitals included, number of beds, number and type of wards/specialties/services included).
- > Each study site/country to describe the existing SARI surveillance system in place.
- Each study site/country to describe the study population for IVE and for CVE.
- > Each study site/country to describe target group(s) for vaccination and order/timeline of vaccination by group (if known).
- > Each study site/country to describe the epidemiological situation (incidence, number of COVID-19 or influenza hospitalisations, mortality).

3.3 Study period

The study period for CVE starts with the availability of COVID-19 vaccine(s) and a SARS-CoV-2 variant of concern circulating in the participating country. In order to determine SARS-Cov-2 variant dominance, ECDC surveillance data on variants of concern can be used. In the context of vaccination campaign performed in autumn 2023 to which this protocol refers, and with possible spring campaigns for selected groups, the study period for CVE can be more adapted to the IVE methods, with the study period starting at the initiation of the relevant COVID-19 vaccination campaign within a country/region. As COVID-19 and vaccination campaigns evolve, the study period can be adjusted accordingly. The study period for IVE begins when the seasonal influenza vaccine for the corresponding season becomes available and the influenza season begins in the country/region. The study period finishes at the end of the influenza period which could be defined as the last week in which there was a hospitalised SARI patient positive for influenza, or week 20, depending on which is earliest. Cases and controls are included from the week of onset of the season's first influenza-positive case in each country-specific study.

Participating hospitals carry out the CVE study throughout the year.

- > Each study site/country to define the beginning of the CVE study period (day/month/year).
- Each study site/country to define the beginning and end of the IVE study period (day/month/year) and criteria for defining the IVE study period in their country.
- Each study site/country to specify the start date of their COVID-19 and influenza vaccination campaign, by target group and for the general population, for primary course vaccination. For COVID-19, each site/country should additionally specify dates for each booster dose, by target group (if applicable) and for the general population.

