3.4 Outcomes

COVID-19 vaccine effectiveness studies

The outcome of interest for the primary analysis is SARS-CoV-2 infection in patients of all ages hospitalised with SARI symptoms, laboratory-confirmed by PCR, documented either on admission to hospital or in the 14 days before admission.

Secondary outcomes of interest, in the same patient group, are laboratory-confirmed infections with genetic variants of SARS-CoV-2 and confirmed SARS-CoV-2 patients with severe outcomes (ICU admission, invasive ventilation or death).

Influenza vaccine effectiveness studies

The outcome of interest is laboratory-confirmed influenza in patients of all ages, hospitalised with SARI symptoms.

More specifically, this will be:

- subtype-specific laboratory-confirmed influenza A;
- laboratory-confirmed influenza B overall and, if available, by lineage (B Victoria/B Yamagata);
- laboratory-confirmed influenza by clade (where possible);
- laboratory-confirmed influenza co-infected with SARS-CoV-2 (where possible).

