3.5.5 SARI patients testing negative for SARS-CoV-2/influenza (test-negative controls)

A control will be defined as a hospitalised patient fulfilling the SARI case definition, with a respiratory sample negative for SARS-CoV-2 by PCR (for CVE) or a respiratory sample negative for influenza (for IVE) on admission to hospital.

It is advised that all sites test for both SARS-CoV-2 and influenza during the influenza season, as well as for all other respiratory viruses (as appropriate, depending on time of year), even if they are not participating in IVE. If this is not feasible, then during influenza season all samples that are negative for SARS-CoV-2 should also be tested for influenza (if not already tested at primary care level).

Controls that are negative by PCR but have Ct results suggestive of COVID-19⁶, and those with prior SARS-CoV-2 infection in the three months before admission, may be excluded as controls in sensitivity analyses (see Section 3.5.7 'Exclusion criteria').

- A study site/country measuring only CVE should indicate which testing strategy they will use (testing all samples for both SARS-CoV-2 and influenza, or only testing for influenza in those negative for SARS-CoV-2).
- > Each study site/country to indicate whether they can test for other respiratory viruses, only SARS-CoV-2 and influenza, or only SARS-CoV-2.

Other control groups (optional)

During periods when respiratory viruses are in low circulation, the number of SARI patients testing negative for SARS-CoV-2/influenza may be limited. Some sites may therefore wish to include other control groups, either in addition to SARI controls or as an alternative, and these must be recruited throughout the whole study period.

Examples of other control groups include:

- Patients testing PCR-negative to all respiratory viruses;
- Patients testing PCR-positive to respiratory viruses other than influenza (if IVE) or SARS-CoV-2, e.g. rhinovirus, respiratory syncytial virus (RSV), etc.; noting that patients with seasonal coronaviruses are excluded for CVE;
- Patients hospitalised with non-SARI related symptoms matched by time, age group and, if possible, underlying conditions:
 - Example source of hospitalised non-SARI cases: hospital wards admitting patients without COVID-19.
 Primary care: selection of GP patients belonging to the hospital catchment area and vaccination target
- group matched by time and age group:

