- use of medications for chronic conditions (e.g. statins, for IVE);
- Other stratifications may be included.

Virus variant-specific outcomes will be used, if available and feasible at the time of analysis.

A sufficient sample size should be planned in order to ensure enough individuals in each stratum for a precise estimate. Effect modification will be assessed comparing the OR across the strata of the potential effect modifiers. Confounding will be assessed by comparing crude and adjusted OR for each potential confounder.

Multivariable analysis

A multivariable logistic regression analysis will be conducted to control for negative and positive confounding. Odds ratios and standard errors will be obtained. Variables will be tested for multicollinearity. Interactions will be tested using the likelihood ratio test or Wald's test and will be included in the model if significant at the 5% level. Factors other than statistical significance (prevalence of exposure, magnitude of OR) will also be used as criteria for inclusion of a variable or an interaction term. If possible, a variable for sex, age and onset time should always be included in the model.

Continuous variables

Continuous variables in the COVID-19/influenza datasets include age, time of onset of symptoms, and hospitalisations in the past 12 months. These variables can be coded as categories (e.g. age group, week of symptom onset, etc.) However, when coding continuous variables as categories, information may be lost, or introduce residual confounding and increase the standard error of the model. Tests will be carried out to see if these variables could be coded as a linear term, polynomial or a spline. In addition, a balance will be sought between simplicity of a model (so a non-expert can understand it), precision and a model that estimates the vaccine effect with the least bias.

Identifying heterogeneity, testing for heterogeneity

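### IVE by subtype, lineage and clade uses one any-influenza inclusion window, so early-season controls bias crude and weakly time-adjusted estimates downwards if coverage is still rising

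*Protocol*

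**What the plan says.** **Window.** Protocol Section 3.3 ties the start of the IVE period to vaccine supply and the start of the season: "The study period for IVE begins when the seasonal influenza vaccine for the corresponding season becomes available". Cases and controls enter from the week of the "first influenza-positive case in each country-specific study". The period ends at "the last week in which there was a hospitalised SARI patient positive for influenza, or week 20", whichever is earlier. Neither limit names a type or subtype.

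**Outcomes.** Section 3.4 lists "subtype-specific laboratory-confirmed influenza A", "laboratory-confirmed influenza B overall and, if available, by lineage (B Victoria/B Yamagata") and "laboratory-confirmed influenza by clade (where possible").

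**Controls.** Section 3.5.5 requires "a respiratory sample negative for influenza (for IVE) on admission to hospital". The same group serves every virus-specific outcome, and no section limits it to the weeks in which the analysed virus was found.

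**Time.** Section 3.5.5 recommends matching or adjusting for time because circulation and coverage change. Section 5.1.9 says onset date will be used for adjustment. Annex 2 wants sex, age and onset time in every model, but only where possible. On the form of continuous variables it says: "Tests will be carried out to see if these variables could be coded as a linear term, polynomial or a spline". Table 7, given as a layout example, shows a cubic spline for onset date. It also has a crude row and rows adjusted only for sex, chronic condition or age.

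**The concern.** Section 3.3 already leaves out controls from before influenza appears, since nobody could then have been a case. The same reasoning is not carried to the virus-specific outcomes. If influenza B arrives months after influenza A, the influenza B analysis still takes controls from the early influenza A weeks.

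Those weeks lie closest to the vaccination campaign. If coverage is then still rising, the early controls lower control coverage, the odds ratio moves up, and IVE looks too low. They also swell the number of controls reported. They can help to meet Annex 2's criterion of five records per cell without adding information on that virus. Annex 2 judges confounding by comparing crude with adjusted odds ratios, so an avoidable artefact would enter that comparison.

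**Working it through.** **The plan's own figures.** The protocol gives no figure for this bias, no weekly coverage and no subtype timing. The nearest figure is in Table 5: odds ratio (OR) 0.5, control coverage 0.5, lower limit 10 points below the estimate, 983 cases. It reproduces. Case coverage is p1 = OR·p0/(1 − p0 + OR·p0) = 0.25/0.75 = 1/3. Then n = 1.96² × [1/(0.5 × 0.5) + 1/(1/3 × 2/3)] / ln(0.6/0.5)² = 3.8415 × 8.5 / 0.03324 = 982.3, rounded up to 983. Table 5 assumes one coverage for all controls and has no time structure.

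**Assumed inputs.** The window has 24 weeks, with equal numbers of controls per week. Coverage rises in a straight line from 15% in week 1 to 50% in week 12 and is then flat. True IVE is 50% throughout.

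**Crude IVE, virus from week 13.** Crude IVE = 1 − (case odds of vaccination)/(control odds of vaccination).
- Case odds: (1/3)/(2/3) = 0.5.
- Mean control coverage, all 24 weeks: (12 × 0.325 + 12 × 0.5)/24 = 0.4125, so odds 0.7021.
- All controls: 1 − 0.5/0.7021 = 28.8%.
- Controls from weeks 13 to 24 only: odds 1, so 1 − 0.5/1 = 50%.

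The same formula under other assumptions, virus from week 13, all controls kept:

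| Coverage | Mean control coverage | Crude IVE | True IVE |
|---|---|---|---|
| 15% to 50% | 0.4125 | 28.8% | 50% |
| 15% to 50% | 0.4125 | −42% | 0% |
| 30% to 50% | 0.4500 | 38.9% | 50% |
| 45% to 50% | 0.4875 | 47.4% | 50% |
| 50%, flat | 0.5000 | 50.0% | 50% |

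Half of the controls (12 of 24 weeks) precede the virus here; with a start in week 9 it is a third (8 of 24).

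**With time adjustment.** Logistic regressions on expected counts, all controls kept, coverage 15% to 50%, true IVE 50%, with the virus's cases spread evenly or as a bell over its own weeks:

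| Virus starts | Crude | Linear onset time | Spline | Crude, virus's own weeks |
|---|---|---|---|---|
| Week 13 | 29% | 47-48% | 50% | 50% |
| Week 9 | 29-32% | 44-45% | 50% | 48-50% |

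The linear result depends on the epidemic curve. With a sharper peak after a week-9 start it falls to about 41%. A second set used 26 weeks, coverage 10% to 50% by week 9, and the virus from week 9. Mean control coverage is then (2.20 + 18 × 0.5)/26 = 0.431. Crude IVE is 33.9% and linear 39.5%, while week strata, four-week periods and a spline all give 50.0%. For a true IVE of 30% the same setting gives 7.5% crude and 14.5% linear. Across all scenarios of that set, the three flexible forms stayed within 0.6 points of the truth.

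**Why flexible adjustment works.** In a week with no case of the virus, both case cells are zero. That week adds nothing to the numerator or the denominator of a week-stratified odds ratio. A linear term cannot represent no cases followed by a sudden start, so early controls still influence the fit.

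**Where flexibility may be lost.** One Annex 2 criterion is about 10 cases (or controls, if fewer) per parameter. Vaccination, sex, linear age and linear onset time make four parameters, so 40 cases. Replacing the linear time term by a three-parameter spline makes six, so 60. Site effects would add to both. A lineage with 40 to 59 cases would therefore pass with the linear term and fail with the spline.

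**The case against.** A reader might infer that every virus-specific IVE from this study will be pulled down. The documents do not support that. The multivariable model is the final step and gives the adjusted IVE; the crude figure is a first step. Onset-date adjustment is planned, Table 7 shows a spline for it, and no row of that table shows a linear time term. With a spline the bias is practically nil.

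Nor does Annex 2 simply accept a linear term; it says the form will be tested. In the week-9 scenario with an assumed 60 cases and 300 controls, a likelihood-ratio test of linear against spline gives p of about 0.00002, so the planned check would normally reject the linear form. The size of the bias rests on assumed coverage: Section 3.5.5 says only that coverage changes, and by the first influenza case much of the campaign may be over.

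A contrast with COVID-19 is also tempting, because Section 3.7 mentions periods dominated by a subvariant. It says only that such periods may be defined, and sets no rule on controls that influenza lacks.

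These arguments hold for a well-populated, flexibly adjusted model. They do not reach the crude results, the Table 7 rows without onset date, or sparse models. For sparse data, Annex 2 itself suggests modelling continuous variables differently, and onset time is required only where possible. Nor is this a detail merely left to an analysis plan: Section 3.3 states a window, and states it for influenza as a whole.

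**Conclusion.** The inclusion window is set at the wrong level for the virus-specific outcomes. Under the assumed rise in coverage from 15% to 50% over 12 weeks and a true IVE of 50%, crude IVE is about 29-32% and linear-time IVE about 44-48%, lower still with a sharp epidemic. A spline or week-level term gives about 50%. The crude bias is 2 to 3 points if coverage rises only from 45% to 50%, and nil if coverage is flat. The downward direction depends on coverage still rising before the virus arrives, which is plausible but not stated in the protocol.

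The risk therefore lies in sparse lineage and clade analyses where onset time is dropped or simplified, in the estimates shown without onset-date adjustment, and in the crude-versus-adjusted comparison. This is worth correcting, but it does not undermine a main adjusted analysis that uses a flexible time term.

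**What to change.** In Section 3.3 and Annex 2:
- Limit each (sub)type-, lineage- and clade-specific IVE analysis to patients with onset between the first and last week of a case of that virus, per site or country. Keep the any-influenza window for overall influenza.
- Keep onset time in every virus-specific model as a flexible term (spline or period), not linear only. The window alone is not enough if coverage still rises inside it: in the week-9 example the restricted crude IVE can be 48% against a true 50%.

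The cost is some wording and one filter per outcome. Fewer controls will be listed, by a third to a half in the 24-week examples, but those removed add essentially no information on the effect. At sites with few cases of a virus, the window will depend on a single early or late case; setting it by country lessens this.
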